#### 3.2 Study Endpoints

#### 3.2.1 Primary Study Endpoints

This pilot study is designed to test the acceptability and feasibility of SASI. The primary endpoint, acceptability, will be evaluated by the percentage of participants rating SASI as acceptable (overall acceptability survey scores greater than 21), neutral (overall acceptability survey scores equal to 21), and unacceptable (overall acceptability survey scores less than 21) at each of two time points (pre- intervention and post intervention). The feasibility endpoints will be determined by the 1) recruitment rate: the percentage of potential participants screened in order to enroll 60 participants 2) attrition rate: the percentage of enrolled participants completing the 18-week study. Participants will be considered withdrawn after 4 weeks of not responding to phone calls/emails during the intervention and the 3) protocol adherence rates: the percentage of participants completing greater than or equal to 4 daily sleep diary entries per week for 80% or more of the intervention period.

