Study Sites	NYU Langone Health NYU Rory Meyers College of Nursing

Version Date: September 27, 2019

	Bellevue Hospital [name] in C/D Building, 4th Floor New York, NY.

Drug/Device Template Version: 13 JUN 2016

Number of participants	We will screen approximately 220 individuals for a final sample of N= 60 participants. Of these 220 participants, we anticipate that 65% will become ineligible through the multi-stage screening process and 20% will be lost to attrition during the intervention leaving 60 participants with evaluable data.
Description of Study Intervention/Procedure	SASI is based on Cognitive Behavioral Therapy for Insomnia (CBTI). Like CBTI, SASI extends sleep based on sleep efficiency (the proportion of time spent sleeping during a sleep episode). Bedtimes and wake times will be prescribed each week for each participant and allow for gradual increases in sleep opportunity. Bedtimes will be set 15 minutes earlier each week provided sleep efficiency remains >90%. Earlier bedtimes will extend sleep duration by increasing the opportunity for sleep. Wake times will not be changed because wake times are often determined by external demands, such as work schedules.
Reference Therapy	Not applicable.
Key Procedures	Surveys, patient reported outcomes, anthropometric measurements, blood pressure measurement, daily sleep diaries, wrist accelerometry, blood draw (3 ml CTSI visit 1), open-ended interview.
Statistical Analysis	Primary endpoints: 1) Acceptability based on the percentage of pre and post intervention acceptability surveys with total scores < 21 (unacceptable), 21 (neutral), greater than 21 (acceptable). 2) Feasibility will be based on recruitment, retention, and study protocol adherence rates.

Version Date: September 27, 2019

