## 4 Study Enrollment and Withdrawal

To reach a final sample of N= 60, we will recruit 220 individuals. Of these, we anticipate that 65% will become ineligible through the multi-stage screening process and 20% will be lost to attrition during the intervention leaving 60 participants with evaluable data.

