## 12.2 Statistical Hypotheses

The sample size is too small to make inferences about relationships evaluated in the pilot study to the larger population of middle aged adults with MetS. For the primary aim, acceptability will be evaluated by the percentage of participants rating SASI as acceptable (overall acceptability survey scores greater than 21), neutral (overall acceptability survey scores equal to 21), and unacceptable (overall acceptability survey scores less than 21) on the Acceptability Survey at each of two time points (pre-intervention and post intervention). Feasibility will be evaluated by the 1) recruitment rate: the percentage of potential participants screened in order to enroll 60 participants with evaluable data, 2) attrition rate: the percentage of enrolled participants completing the 18-week study. Participants will be considered withdrawn after 4 weeks of not responding to phone calls/emails during the intervention, and the 3) protocol adherence rates; the percentage of participants completing greater than or equal to 4 daily sleep diary entries per week for 80% or more of the intervention period. For the secondary endpoints, paired t-tests will be used to compare the mean preintervention and mean post-intervention estimates for SAFTEE scores, physical activity, sedentary behavior, diet quality, smoking, alcohol use, affective well-being, morning fatique, evening fatique, and self- regulation measurements. For the exploratory endpoints of perceived barriers and facilitators of SASI, bivariate correlations between specific socio-ecological factors and sleep duration change will be identified. The qualitative data from the post intervention interviews will be analyzed using content analysis. Content analysis includes a line- by-line review that yields clusters of data that are coded. This coding is linked to interview questions. Summarization of coding will be performed across individual interviews, and subsequently crossclassified to yield a rich descriptive analysis. Emerging themes within and across interviews will be identified, and review of fit with data verified.

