### 12.4.2 Analysis of the Primary Efficacy Endpoint(s)

For Aim 1: Acceptability will be based on the pre- and post-intervention acceptability survey measurements. The acceptability survey is an ordinal scale with higher scores indicating greater acceptability. Results will be reported as a categorical outcome indicating the count and percentage of participants rating SASI at the pre-intervention assessment as well as the post intervention assessment as acceptable (total scores greater than or equal to 21), neutral (total score equal to 21), and unacceptable (total scores less than 21).

Feasibility will be based on recruitment, retention, and study protocol adherence. Recruitment will be measured as the number and percentage of participants screened and their determination as eligible or ineligible based on inclusion/exclusion criteria. Results will be reported as a recruitment rate indicating the count and percentage of participants eligible and ineligible. Attrition rates will be reported as the number

and percentage of participants who withdraw from the study. Attrition rates >20% will suggest lack of feasibility. Recruitment and attrition rates will also be examined for differences in specific subgroups. Study protocol feasibility will be indicated by percentage of participants providing at least 4 work day sleep diaries per week for greater than or equal to 80% of the intervention period.

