### 12.5 Sample Size

Our final sample size is N=60. To achieve this, it is anticipated that 220 interested potential participants will go through the telephone screening procedures. The reason we will need to screen 220 is because OSA is often a co-morbid condition with MetS and we anticipate 65% of participants screened will become ineligible after the initial CTSI visit. We also anticipate that 20% will not complete the study protocol.

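### The primary recruitment rate has no single definition, and the version in section 12.4.2 is an eligibility rate that cannot show how many eligible people decline

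*Combined protocol and SAP*

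**What the plan says.** Three parts of the current text describe the recruitment rate.

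- Section 3.2.1 (Primary Study Endpoints): "recruitment rate: the percentage of potential participants screened in order to enroll 60 participants". The attrition rate listed next to it takes enrolled participants as its base.
- Section 12.2 (Statistical Hypotheses) has the same phrase with an added condition: "the percentage of potential participants screened in order to enroll 60 participants with evaluable data".
- Section 12.4.2 (Analysis of the Primary Efficacy Endpoint(s)) measures recruitment by whether screened people meet the inclusion and exclusion criteria: "Results will be reported as a recruitment rate indicating the count and percentage of participants eligible and ineligible".

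The Protocol Summary gives the scale: "We will screen approximately 220 individuals for a final sample of N= 60 participants". Section 4 supplies the losses: "we anticipate that 65% will become ineligible through the multi-stage screening process and 20% will be lost to attrition during the intervention". The same section puts the evaluable total at 60. Section 12.5 places the 220 at the telephone stage: "it is anticipated that 220 interested potential participants will go through the telephone screening procedures".

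The protocol also foresees people who qualify but do not join. Telephone screening (under 7.3.1) leads to a visit only for those who are both eligible and interested. Section 7.3.2 obtains consent only if the person wishes to give it. Section 15.3.2 cancels the enrollment visit for a candidate who prefers not to go on.

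**The concern.** A recruitment rate should say what share of the people approached or screened end up in the study. The 12.4.2 rule does not do that. It sorts screened people by the eligibility criteria alone, so an eligible person who refuses counts the same as one who takes part. Willingness to join a weekly, home-based programme is part of what a feasibility pilot needs to learn, and this rate cannot show it.

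The 12.2 wording has a different problem. A yield of participants with evaluable data already includes losses during the intervention, and those losses are also reported as attrition. The two rates overlap.

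The protocol says (sections 1.1 and 1.2) that the pilot data will support a fully powered randomised trial. If the definition is left open, it can be settled after the counts are known, and a planner who takes the figure forward may not know which losses it contains.

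**Working it through.** **Inputs.** Screened: 220 (Protocol Summary; section 12.5). Ineligible: 65%, and attrition: 20% (section 4). Final sample: 60 evaluable (section 4). Refusal among eligible people: not given, so treated as an assumption with a range.

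**Reproducing the plan.**
- Eligible: 220 × (1 − 0.65) = 77.
- Evaluable: 77 × (1 − 0.20) = 61.6, against the stated 60.
- In reverse: 60 / 0.80 = 75 must enter, and 75 / 0.35 = 214.3 must be screened, against the stated 220.

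The plan is consistent when the losses are applied in sequence. Subtracting both percentages from 220 would leave 220 × 0.15 = 33, which does not match.

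**Rates from this one planned log.**
- Evaluable over screened (section 12.2): 60/220 = 27.3%, or 61.6/220 = 28.0% with the unrounded product.
- Eligible over screened (section 12.4.2): 77/220 = 35.0%.
- Section 3.2.1: 60/220 = 27.3% if its 60 is set against the planned 220. It is 77/220 = 35.0% if everyone who enters is counted and nobody declines. If screening stops at the 60th enrolment, 60 / 0.35 = 171.4, so 172 are screened and 60/172 = 34.9%.

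**Are 60 enrolled and 60 evaluable the same?** Not with 20% attrition. Sixty enrolled leaves 60 × 0.80 = 48 evaluable, while 60 evaluable needs 75 enrolled.

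**Effect of refusal.** Assume a fraction r of the 77 eligible people decline, so that enrolled = 77 × (1 − r).

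| r (assumed) | Enrolled | Enrolled / 220 | Section 12.4.2 rate |
|---|---|---|---|
| 0% | 77.0 | 35.0% | 35.0% |
| 10% | 69.3 | 31.5% | 35.0% |
| 20% | 61.6 | 28.0% | 35.0% |
| 30% | 53.9 | 24.5% | 35.0% |

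The plan has little room for refusal: 77 are expected to be eligible and 75 are needed, a margin of 2/77 = 2.6%.

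**Effect of the overlap, if both rates are used in planning.** Someone who needs 60 evaluable and inflates to 75 for dropout should divide by 0.35 and screen 214.3 (no refusal). Dividing by the 12.2 yield gives 75 / 0.28 = 267.9, or 75 / (60/220) = 275. That is 25% to 28% more screening than needed, because dropout has been allowed for twice.

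**The case against.** The best defence is that the wordings differ less than they seem to. Section 4 describes the 60 as evaluable and section 12.5 calls 60 the final sample size, so 12.2 may only complete a shorthand in 3.2.1. This is a fair reading. A reader might infer that the plan holds three incompatible definitions with three results, but the planning figures give only two values. The reading does not remove the problem, though: section 3.2.1 itself separates those enrolled from those completing, and 12.4.2 remains a different quantity.

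A reader might also infer that 12.2 counts every dropout twice. The documents do not support that as an error of counting. A yield to evaluable data reported beside an attrition rate is an overlap, and it misleads only if someone applies both in a later calculation.

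Three further points stand. Only attrition carries a feasibility threshold (above 20%, section 12.4.2). Section 12.4.2 asks for counts as well as percentages, so eligible over screened would at least be transparent. Section 12.1 calls this chapter an overview and defers to a formal SAP, where the definition could still be settled. These limit the consequence, but none of them gives the recruitment rate a numerator and a denominator.

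**Conclusion.** The point holds as an inconsistency in a primary feasibility endpoint. Section 12.4.2 labels an eligibility rate as recruitment, while 3.2.1 and 12.2 describe reaching 60 participants at stages that coincide only without attrition. On the plan's own figures the reported value would be about 27-28% or 35%, a difference of 7 to 8 percentage points from the same log.

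The two values rest only on the documents' planning assumptions. The refusal results rest on an assumed range of 0% to 30% and show direction and scale, not a forecast. It would go too far to say that a feasibility conclusion could flip, because no recruitment threshold exists. The effect is on what is reported and what is carried into the later trial.

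The word enrolled is also unsettled. Section 7.3.2 calls CTSI Visit 1 the enrollment visit, but short sleep, and with it eligibility, is confirmed only in week 3 (section 7.3.3.3). The base is stated loosely too: section 4 says 220 will be recruited, section 6.1.1 puts about 220 in the study, and section 12.5 has 220 telephone-screened.

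**What to change.** Use one formula in sections 3.2.1, 12.2 and 12.4.2: recruitment rate = number confirmed eligible at week 3 who start SASI / number telephone-screened.

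- Report two component rates separately, with 95% confidence intervals: eligibility (eligible / screened) and uptake (started / eligible).
- Remove the evaluable-data condition from 12.2, so that losses after the start appear only in attrition.
- Define enrolled once and use that meaning in the attrition denominator. Otherwise recruitment would count those who start the intervention while attrition could still count everyone who consented at CTSI Visit 1.
- State the 220 consistently as telephone-screened.
- Record the stage at which a person declines. Someone who declines before week 3 has not been fully assessed, and the uptake denominator must say how such people are handled.

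No visit, procedure or participant burden changes. Most of the work is wording, but the screening log may need a code for declining. Section 10.8 says that screening data in REDCap will include reason for exclusion and does not mention refusal, and section 4.4.6 has the team discard information on people identified through Epic who do not wish to take part. A count by stage without identifiers would be enough. The change should be made before the counts are analysed.

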## **Protocol Summary**

blocoi Summary	
Title	P20 Extending Sleep to Reverse Metabolic Syndrome in Middle-Aged Adults: Acceptability and Feasibility of a Sleep Intervention
Short Title	P20 [name] Pilot
Brief Summary	This pilot study will test the acceptability and feasibility of a sleep extension intervention in community-dwelling, short-sleeping, racially/ethnically diverse middle-aged adults with MetS. Baseline sleep habits will be assessed and used to guide individualized strategies to extend sleep. A 1-group pretest-posttest study design will test the efficacy of this 18-week study (2 weeks of baseline data collection, 1 week of study intervention planning, 12 weeks of sleep intervention delivery, final follow up 3 weeks after last day of the 12-week intervention) on sleep duration, MetS risk behaviors (reduced physical activity, increased sedentary behavior, poor diet quality), symptoms associated with MetS risk behaviors (poor affective well-being, fatigue), and self-regulation. Socio-ecological barriers and facilitators to the intervention will be identified using a quantitative and qualitative approach.
Phase	Pilot study
Objectives	Primary Objective: Test the feasibility and acceptability of a self-management for adequate sleep intervention (SASI) in community-dwelling, short-sleeping, middle-aged adults with MetS.  Secondary Objective: Assess the preliminary efficacy of SASI on sleep duration, MetS risk behaviors (physical activity, sedentary behavior, diet quality), symptoms associated with MetS risk behaviors (affective well-being, fatigue) and self-regulation.  Exploratory Objective: Explore the perceived barriers and facilitators of SASI (e.g., socio-ecological factors) barriers and facilitators of SASI (e.g., socio-ecological factors).
Methodology	1-group pre-test and post-test pilot study
Endpoint	Primary Endpoints: 1) Acceptability (pre-intervention and post- intervention, 2) Feasibility (recruitment rate, retention rate, protocol adherence rate).  Secondary Endpoints: 1) sleep duration, 2) physical symptoms, 3) physical activity, 4) sedentary behavior, 5) diet quality, 6) affective well– being, 7) self-regulation.
Study Duration	3 years
Participant Duration	18 weeks
Duration of behavioral intervention	12 weeks
Population	Participants will be male and female, 35-60 year old, short-sleeping adults from diverse racial/ethnic groups with the Metabolic Syndrome in the greater New York City area.

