#### 4.5.1 Reasons for Withdrawal or Termination

Participants are free to withdraw from participation in the study at any time upon request. An investigator may terminate participation in the study if:

- Any clinical adverse event (AE), laboratory abnormality, or other medical condition or situation occurs such that continued participation in the study would not be in the best interest of the participant
- The participant meets an exclusion criterion (either newly developed or not previously recognized) that precludes further study participation.
- The participant does not respond to phone calls/emails for 4 weeks during the intervention.

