#### 4.5.2 Handling of Participant Withdrawals or Termination

Participants will be considered withdrawn if they cannot be contacted for 4 weeks during the intervention using all of the contact information collected. No further efforts will be made to contact the participant and that participant will be considered lost to follow-up. Abrupt termination of participation in the study intervention poses no safety risk to participants. As this study is minimal risk, efforts will not be made to collect safety and efficacy data after withdrawal.

Any data collected before withdrawal from the study will be retained for analysis, and no new data will be collected. If the participant requests that data be destroyed, all paper records will be shredded, and any data already processed into computer files will be removed. However, if results based on the participant's data have been submitted for publication or presentation before the request is made, the results cannot be removed from the publication or presentation.

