### 12.4.5 Adherence and Retention Analyses

Adherence and retention are the primary endpoints for this pilot study.

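### The primary feasibility measure called attrition rate is the percentage completing in 3.2.1 and 12.2 but the percentage withdrawing in 12.4.2; the two are not complements, and the denominator is ambiguous.

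*Combined protocol and SAP*

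**What the plan says.** The same measure appears under two names and two definitions.

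- **Protocol Summary** lists the feasibility endpoints as "Feasibility (recruitment rate, retention rate, protocol adherence rate", and **12.4.5** states "Adherence and retention are the primary endpoints for this pilot study". Both use the term retention.
- **3.2.1** and **12.2** call it attrition but define it by completion: "attrition rate: the percentage of enrolled participants completing the 18-week study".
- **12.4.2** reports attrition as the number "and percentage of participants who withdraw from the study. Attrition rates >20% will suggest lack of feasibility". It does not name a denominator.

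The planning text uses loss and non-completion for the same 20%. Section 4 has "20% will be lost to attrition during the intervention leaving 60 participants with evaluable data", and 12.5 has "We also anticipate that 20% will not complete the study protocol".

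There are two stated routes by which a participant comes to be withdrawn without an investigator's decision. One is by request: "Participants are free to withdraw from participation in the study at any time upon request" (4.5.1). The other is by silence: "Participants will be considered withdrawn if they cannot be contacted for 4 weeks during the intervention" (4.5.2, and to the same effect in 3.2.1, 4.5.1 and 12.2).

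On timing, section 3.1 gives two weeks of baseline, a planning week in which eligibility is confirmed, the intervention in weeks 4 to 15, and a final visit up to three weeks after that. On enrollment, 7.3.2 calls CTSI Visit 1 the enrollment visit. Section 7.3.3.3 decides eligibility for the intervention in week 3 and uses the word retained for people who pass that check. The depression text in 10.8 speaks of being enrolled in the intervention phase, a later event.

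**The concern.** A primary feasibility measure with a numerical mark attached should have one definition. Here the endpoint section and the analysis section point in opposite directions, and swapping the label does not fully reconcile them. Three questions are left open: whether the reported rate is completion or withdrawal; how to class people who neither complete nor withdraw; and which group is divided by.

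At stake is the feasibility reading passed to the randomized trial that this pilot is meant to inform (1.1 and 1.2). A late non-completer counts against the study under one section and not under another, and planned attrition lies exactly at the mark where that difference matters.

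**Working it through.** **1. Reproduce the planned sample.** Inputs from section 4 and 12.5: 220 screened, 65% found ineligible, 20% lost, 60 left.

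- Forward: 220 x (1 - 0.65) = 77; 77 x (1 - 0.20) = 61.6, against 60 stated.
- Backward: 60 / 0.80 = 75; 75 / 0.35 = 214.3, so 215, against 220 stated.
- Taking both percentages off the 220 gives 220 x (1 - 0.65 - 0.20) = 33, which does not fit.

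The plan's own 20% is therefore a proportion lost among the roughly 75 to 77 who pass screening.

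**2. Apply both definitions to the planned outcome (60 completers of 75).**

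- 3.2.1 and 12.2: 60 / 75 = 80%.
- 12.4.2, with all 15 losses as withdrawals: 15 / 75 = 20.0%, which is not above 20%.

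**3. Check whether they are complements.** The four-week silence rule runs only within weeks 4-15. Silence starting in week 13 has lasted three weeks (13, 14, 15) when the intervention ends, so the rule cannot be met. The 18-week study includes a final visit after week 15. Someone silent from week 13 who never attends, or who finishes week 15 and misses that visit, is a non-completer under 3.2.1 and 12.2. Unless they ask to withdraw, they are absent from the 12.4.2 count.

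**4. Find the cut.**

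| Participants | 15 losses | 16 losses |
|---|---|---|
| 75 | 20.0%, not above | 21.3%, above |
| 77 | 19.5%, not above | 20.8%, above |

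One person is enough: with 77 participants, 15 withdrawals and one missed final visit, withdrawal is 19.5% and non-completion 16 / 77 = 20.8%.

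**5. Chance that the two counts give different readings.** Let L be all non-completers, L ~ Binomial(n, p), of whom u are unclassified. The readings differ when L is at least 16 and L - u is at most 15, that is 16 <= L <= 15 + u. The documents give no value for u; it is assumed here to be 1 to 3 (with u = 0 the chance is nil). The documents' planning value is p = 20%; the other rates are shown for range. Each cell spans n = 75 and n = 77.

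| True non-completion p | u = 1 | u = 2 | u = 3 |
|---|---|---|---|
| 10% | 0.2% | 0.2-0.3% | 0.3% |
| 15% | 4% | 6-7% | 8-9% |
| 20% | 11% | 20-21% | 28-29% |
| 25% | 8% | 17-18% | 27-29% |
| 30% | 2-3% | 5-7% | 10-12% |

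**6. Denominator.** The number attending Visit 1 is not given. Taking 100 or 150 as assumed values, the same 15 withdrawals are 15 / 100 = 15.0% or 15 / 150 = 10.0%, against 20.0% of 75. Sixty completers are 60% or 40%, against 80% of 75. Counting from Visit 1 thus lowers the withdrawal rate and also lowers the completion rate, because people found ineligible in week 3 stay in the denominator.

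**The case against.** The intended meaning can largely be recovered. Section 12.4.2 is correctly oriented on its own, and its threshold makes sense for withdrawals. The study schematic treats the two-week baseline as part of screening, section 4 places the 20% loss during the intervention, and the planned 60 reproduces only on that reading. A sensible analyst would not report 80% completion as 80% attrition. All of this stands, so a reader who infers that the planned outcome would be declared infeasible goes further than the documents do. The planned 20% is not above 20% either.

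A reader might also infer that no denominator is given. That is not so: 3.2.1 and 12.2 name enrolled participants. It is missing only in 12.4.2, and the remaining problem is what enrolled means.

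The unclassified group arises only because 12.4.2 counts withdrawals; under 3.2.1 these people are plainly non-completers. That is fair, and makes the gap part of the same conflict rather than a separate defect. But it also shows that correcting the label in 3.2.1 and 12.2 would leave 12.4.2 counting something else.

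Finally, the 11-29% figures are computed with true non-completion exactly at the cut. This is right. Twenty percent is the plan's own value, but the figures are conditional on it, and at 10% the issue nearly vanishes.

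**Conclusion.** The contradiction is certain: it is in the text of 3.2.1 and 12.2 against 12.4.2, and at the planned outcome it is 80% against 20.0%. That the two definitions are not complements follows from the documents' timing rules. The ambiguity of enrolled is also real, though the sample-size arithmetic favors the week-3 group.

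The practical size is less certain. It rests on an assumed one to three unclassified non-completers and a binomial count among 75 to 77 people. On that basis the reading changes with probability about 11-29% at 20% true non-completion, 4-9% at 15%, 8-29% at 25%, 2-12% at 30% and at most about 0.3% at 10%.

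This should be corrected, but its consequence is limited. The pilot has one arm, the mark only suggests lack of feasibility, counts are to be reported beside the percentage, and section 12.1 says a formal SAP is still to be written.

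**What to change.** Use one definition in 3.2.1, 12.2, 12.4.2 and the formal SAP:

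- Retention = participants completing the final visit / participants confirmed eligible in week 3.
- Attrition = 1 - retention. Everyone in that denominator without a final visit counts as lost, whatever the reason.
- Apply the >20% mark to this attrition rate only.
- Report separately, as counts and as percentages of those consented, (a) people found ineligible after consent and (b) people who withdraw before the week-3 decision.
- In 7.3.3.3, call those who pass the check participants confirmed eligible, so that retained keeps one meaning.

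The four-week contact rule can stay as it is. The week-3 denominator is a choice. It matches the sample-size arithmetic, but the 18 weeks named in 3.2.1 also cover weeks 1 to 3.

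The cost is wording; no new data are needed. The effect on the reported figure can go either way. Counting late non-completers makes attrition slightly less favorable, while leaving withdrawals before week 3 out of the denominator may make it more favorable. That is why the latter need their own line in the report.
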